6.3.3. HBeAg Serology Results

A summary table will be provided for HBeAg-related serology results for participants on active treatment within each cohort (5, 6, and 7), and for all CHB participants assigned to placebo for the FAS (participants with HBeAg positive at baseline). The proportion of participants who have ever had HBeAg loss, confirmed HBeAg loss, HBeAg loss with HBeAb seroconversion, HBeAg loss with HBeAb seroreversion, and HBeAg loss reversion with or without HBeAb seroconversion will be summarized.

HBeAg-related terminology is defined similarly to the HBsAg-related terminology.

No statistical testing is planned.

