- c Collection of vital signs, physical examinations, and blood/urine samples should be completed prior to investigational product administration.
- d Symptom-driven physical examinations shall be performed as deemed necessary.
- e At the discretion of the investigator.
- f Indicated assessment shall be taken prior to dosing and within 15 to 30 minutes following investigational product administration.
- g Hematology assessments are listed in Section 6.4.5.
- h An FSH test is required for participants assigned female at birth who are younger than 54 years, not on hormonal contraception, and who have stopped menstruating for at least 12 months but do not have documentation of ovarian hormonal failure.
- i For participants assigned female at birth and of childbearing potential. On days of investigational product administration, urine pregnancy testing is also required to determine pregnancy status prior to dosing.
- j Chemistry and liver function assessments are listed in Section 6.4.5.
- k Central laboratory will calculate creatinine clearance.
- l Required for Phase 1b only.

- m Coagulation assessments are listed in Section [6.4.5](#).
- n Participants will be asked to record potential vaccine reactions based on solicited events via diary for 7 days following each administration of investigational product. Review of participant reactogenicity data will occur at each visit after vaccination up to 7 days postdose or beyond for cases with ongoing events after 7 days postdose.
- o To include the assessments of: HBV DNA, quantitative HBsAg, anti-HBsAg antibody, HBcrAg, HBeAg, HBV RNA.
- p Phase 1a: HBV testing is for HBsAg with reflex to HBV DNA, and hepatitis B core antibody. Phase 1b: HBV testing is for HBsAg, hepatitis B core antibody, HBV DNA, and quantitative HBsAg.

Table 3. Schedule of Assessments, Phase 1a – Cohort 8 and Phase 1b - Cohort 7 (Six Total Doses)

Study Period	Screen	Active Dosing															Safety Follow-up									
Study Day		Base-line Day 1	Day 8	Day 15	Day 29	Day 43	Day 57	Day 71	Day 85	Day 99	Day 113	Day 127	Day 141	Day 148	Day 155	Day 169	Day 197 ^a	Day 225	Day 253 ^a	Day 281 ^a	Day 309	ET				
Visit Window (Days)	45 Days	N/A	± 1	± 1	± 3	± 1	± 3	± 1	± 3	± 1	± 3	± 3	± 3	± 3	± 3	± 7	± 7	± 7	± 7	± 7	± 7	± 7	± 7	N/A		
Study Weeks		1	1	2	4	6	8	10	12	14	16	18	20	21	22	24	28	32	36	40	44					
Dosing (PBO or IP) ^b		X			X		X		X		X		X													
Written informed consent; I/E criteria; medical history		X																								

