6.3.5.2. HBV Viral Biomarkers

Phase 1b only: HBV viral biomarkers (HBsAg, HBV DNA, HBV RNA, HBcrAg, and HBeAg) will be collected at the time points indicated in [Table 2](#) and [Table 3](#) and evaluated as needed.

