- If the ALT elevation is confirmed, the central clinical laboratory will conduct reflex testing for HIV, HBV DNA, qualitative HBV serology (HBeAg and HBeAb; HBsAg and HBsAb), HAV IgM, HCV RNA, anti-HDV IgM, HDV RNA, HEV IgM, antinuclear antibody, antimitochondrial antibody, smooth muscle antibody, and liver/kidney microsome

Based on the results of the confirmatory tests, the following study treatment modifications are recommended.

Table 11. ALT Elevation Monitoring and Toxicity Management

Liver Toxicity Criteria	Action
Confirmed, ALT and or AST $\geq 10 \times$ ULN without evidence of hepatic toxicity as defined below	Cohort 5 to 7: Stop investigational product. Evaluate adherence to NA therapy and review recent HBV DNA results. Evaluate for other causes of hepatotoxicity. Participant must be monitored weekly or more frequently if clinically indicated until ALT returns to nadir. Investigative product may be restarted when ALT $< 5 \times$ ULN upon discussion with medical monitor. Dosing may also be reinitiated upon the recommendations of the SRT.
Persistent ALT and or AST $> 2 \times$ baseline and $\geq 5 \times$ ULN without evidence of hepatic toxicity, as defined below	Cohorts 5 to 7: Continue investigative product. ALT should be evaluated every 2 weeks or more frequently as clinically needed, until values return to nadir.
Confirmed ALT and or AST $> 2 \times$ nadir, with evidence of hepatic toxicity, defined as any one of the following confirmed laboratory abnormalities: Total bilirubin $> 2 \times$ baseline or nadir AND $> 2.5 \text{ mg/dL}$ in the absence of Gilbert's disease Elevated INR > 0.5 above baseline AND $>$ ULN Abnormal serum albumin $> 1 \text{ g/dL}$ decrease from baseline	Cohorts 5 to 7: Permanently discontinue investigational product. Evaluate adherence to NA therapy and review recent HBV DNA results. Evaluate for etiology of ALT elevation. Participant should be monitored weekly until ALT $< 5 \times$ ULN, and total bilirubin, INR, and albumin values return to normal or baseline levels. Liver biopsy may be performed based on investigator's clinical judgment to determine etiology.

ALT = alanine aminotransferase; AST = aspartate aminotransferase; DNA = deoxyribonucleic acid; HBV = hepatitis B virus; INR = international normalized ratio; NA = nucleos(t)ide analogue; SRT = Safety Review Team; TAF = tenofovir alafenamide; ULN = upper limit of normal

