Day 15	Day 15	Day 15 [#]	Day 15 [#]
Day 29	Day 29* ^{\$}	Day 29*# ^{\$}	Day 29*# ^{\$}
Day 43	–	Day 43	Day 43
Day 57	Day 57* ^{\$}	Day 57*# ^{\$}	Day 57*# ^{\$}
Day 71	FU-WK2	Day 71	Day 71
Day 85	FU-WK4^{\$}	Day 85*# ^{\$}	Day 85*# ^{\$}
Day 99	–	FU-WK2	Day 99
Day 113	–	FU-WK4*#^{\$}	Day 113*# ^{\$}
Day 127	–	–	Day 127
Day 141	FU-WK12^{\$}	–	Day 141*# ^{\$}
Day 155	–	–	FU-WK2
Day 169	–	FU-WK12*#^{\$}	FU-WK4*#^{\$}
Day 225	FU-WK24*^{\$}	–	FU-WK12*#^{\$}
Day 253	–	FU-WK24*#[#]	–
Day 309	–	–	FU-WK24*#[#]

*Creatinine Clearance (estimated using Cockcroft-Gault method) collected at this subset of visits.

#Viral biomarkers (HBV DNA, quantitative HBsAg, anti-HBsAg antibody, HBcrAg, HBeAg and anti-HBeAg antibody) collected at this subset of visits for participants in Cohorts 5, 6, and 7 (only).

\$ Antibody to HBsAg [Phase 1a participants only].

Table 3-2. Remapped Follow-Up Visits for Vital Signs, Weight, and BMI

Nominal Visit	Cohorts 1, 2	Cohorts 3, 4, 5, 6	Cohorts 7, 8
Last Value prior to first dose date=Baseline	Baseline*#	Baseline*#	Baseline*#
Day 8	Day 8	–	–
Day 15	Day 15	Day 15	Day 15
Day 29	Day 29	Day 29*#	Day 29*#
Day 43	–	Day 43	Day 43
Day 57	Day 57*#	Day 57*#	Day 57*#
Day 64	FU-WK1	–	–
Day 71	FU-WK2	Day 71	Day 71
Day 85	FU-WK4	Day 85*#	Day 85*#
Day 92	–	FU-WK1	–
Day 99	–	FU-WK2	Day 99
Day 113	–	FU-WK4	Day 113*#
Day 127	–	–	Day 127
Day 141	FU-WK12	–	Day 141*#
Day 148	–	–	FU-WK1
Day 155	–	–	FU-WK2
Day 169	–	FU-WK12	FU-WK4
Day 225	FU-WK24*	–	FU-WK12
Day 253	–	FU-WK24*	–
Day 309	–	–	FU-WK24*

*Weight (and the calculation of BMI) performed at this subset of the visits.

“Pre-dose” and “Post-dose” timepoints will be displayed for vital signs that were collected on injection days.

Table 3-3. Remapped Follow-Up Visits for IFNy ELISpot Assay

Nominal Visit	Cohorts 1, 2	Cohorts 3, 4, 5, 6	Cohorts 7, 8
Last Value prior to first dose date=Baseline	Baseline	Baseline	Baseline
Day 15	Day 15	Day 15	–
Day 29	Day 29	Day 29	–
Day 43	–	Day 43	–
Day 57	Day 57	Day 57	Day 57
Day 71	FU-WK2	Day 71	Day 71
Day 85	FU-WK4	Day 85	Day 85
Day 99	–	FU-WK2	Day 99
Day 113	–	FU-WK4	Day 113
Day 127	–	–	Day 127
Day 141	FU-WK12	–	Day 141
Day 155	–	–	FU-WK2
Day 169	–	FU-WK12	FU-WK4
Day 225	FU-WK24	–	FU-WK12

Table 3-4. Remapped Follow-Up Visits for ECGs

Nominal Visit	Cohorts 1, 2	Cohorts 3, 4, 5, 6	Cohorts 7, 8
Last Value prior to first dose date=Baseline	Baseline	Baseline	Baseline
Day 85	–	Day 85	Day 85
Day 141	–	–	Day 141
Day 225	FU-WK24	–	–
Day 253	–	FU-WK24	–
Day 309	–	–	FU-WK24

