6.3.2. HBsAg Serology Results

A summary table will be provided for HBsAg-related serology results for participants on active treatment within each cohort (5, 6, and 7), and for all CHB participants assigned to placebo for the FAS (participants with HBsAg positive at baseline). The proportion of participants who have ever had HBsAg loss, confirmed HBsAg loss, HBsAg loss with HBsAb seroconversion, HBsAg loss with HBsAb seroreversion, and HBsAg loss reversion with or without HBsAb seroconversion will be summarized.

HBV serology definitions:

- **HBsAg loss:** HBsAg changing from positive at baseline to negative at any postbaseline visit.
- **Confirmed HBsAg loss:** HBsAg loss confirmed by any 2 consecutive results.
- **HBsAg loss reversion:** Any postbaseline HBsAg positive result following HBsAg loss.
- **HBsAb seroconversion:** HBsAb changing from negative or missing at baseline to positive at any postbaseline visit.
- **Confirmed HBsAb seroconversion:** HBsAb changing from negative or missing at baseline to positive at any postbaseline visit confirmed by any 2 consecutive results.
- **HBsAb seroreversion:** Any postbaseline HBsAb negative result following HBsAb seroconversion.

Both baseline and postbaseline borderline results for HBeAg, HBeAb, HBsAg, and HBsAb will be imputed as follows:

- HBsAg and HBeAg results reported as “Equivocal” will be considered HBsAg positive and HBeAg positive, respectively. HBsAb and HBeAb reported as “Equivocal” will be considered HBsAb negative and HBeAb negative, respectively for purposes of analysis
- HBsAg result reported as “Positive Confirmed” will be considered HBsAg “Positive”

Missing data will be treated as a nonevent unless otherwise specified (eg, no HBsAg loss, no seroconversion, etc.)

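### The documents disagree on whether HBeAb is measured at scheduled visits in Cohorts 5-7, and the exploratory HBeAb rows in SAP 6.3.3 depend on the answer

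*SAP*

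**What the plan says.** SAP 6.3.3 states that "HBeAg loss with HBeAb seroconversion, HBeAg loss with HBeAb seroreversion, and HBeAg loss reversion with or without HBeAb seroconversion will be summarized". The table is limited to members of the Full Analysis Set who are "participants with HBeAg positive at baseline", and its terms are defined by analogy with the HBsAg terms in SAP 6.3.2. By that analogy, seroconversion follows the HBsAb pattern: "HBsAb changing from negative or missing at baseline to positive at any postbaseline visit". SAP 6.3.2 adds: "Missing data will be treated as a nonevent unless otherwise specified". SAP 5.2 also lists qualitative HBeAb among the baseline disease characteristics.

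On what is measured, the documents differ:

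- SAP Table 3-1, footnote #: "Viral biomarkers (HBV DNA, quantitative HBsAg, anti-HBsAg antibody, HBcrAg, HBeAg and anti-HBeAg antibody) collected at this subset of visits". This applies to Cohorts 5, 6 and 7.
- Protocol Tables 2 and 3, footnote o, which defines the viral-biomarker row: "To include the assessments of: HBV DNA, quantitative HBsAg, anti-HBsAg antibody, HBcrAg, HBeAg, HBV RNA". SAP Tables 12-2 and 12-3 repeat this footnote.
- Protocol 6.3.5.2: "HBV viral biomarkers (HBsAg, HBV DNA, HBV RNA, HBcrAg, and HBeAg) will be collected".
- Protocol Table 10 lists HBeAb among the other laboratory measurements and refers to Tables 1 to 3 for timing.
- Protocol 7.7.4, reflex tests after a confirmed ALT elevation in Cohorts 5 to 7: "qualitative HBV serology (HBeAg and HBeAb; HBsAg and HBsAb".

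SAP 2.3 declares no changes from the protocol-specified analyses, so nothing in the SAP explains the difference.

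**The concern.** The analysis needs a marker that the protocol's visit schedule does not assign to any visit. Sites work from the protocol. If the laboratory order follows footnote o, HBeAb exists only for participants whose ALT elevation triggered the reflex panel. HBeAg itself appears in every version of the panel, so HBeAg loss would still be seen, but the accompanying HBeAb status would not.

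Two distortions would follow. A participant who loses HBeAg and was never tested for HBeAb would be reported in the same way as one tested and found negative. A participant with HBeAg loss whose only HBeAb result is a positive reflex test could be reported as a seroconverter, because a missing baseline is accepted in place of a negative one. The row would then partly reflect who had an ALT elevation rather than who seroconverted.

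**Working it through.** No sample size, power or error rate is involved. The check is a comparison of the lists, a count of scheduled results, and a trace of the scoring rules.

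**Step 1. Where HBeAb is named**

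| Place | HBeAb named? | Gives a time point? |
|---|---|---|
| SAP Table 3-1, footnote # | Yes | Yes, the marked visits |
| SAP 5.2 | Yes | Baseline |
| Protocol Table 10 | Yes | No, defers to Tables 1 to 3 |
| Protocol 7.7.4 | Yes | Only on a confirmed ALT elevation |
| Protocol Tables 2 and 3, footnote o | No | None |
| Protocol Tables 2 and 3, footnote p (HBV testing) | No | None |
| Protocol 6.3.5.2 | No | None |
| SAP Tables 12-2 and 12-3, footnote o | No | None |

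The SAP therefore disagrees with its own appendix as well as with the protocol.

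**Step 2. Scheduled postbaseline HBeAb results per participant**

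Under SAP Table 3-1, counting postbaseline visits marked #:

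- Cohorts 5 and 6: Days 15, 29, 57, 85 and follow-up Weeks 4, 12, 24. That is 4 + 3 = 7.
- Cohort 7: Days 15, 29, 57, 85, 113, 141 and follow-up Weeks 4, 12, 24. That is 6 + 3 = 9.

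Under footnote o read literally: 0 in all three cohorts.

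At the planned 10 participants per cohort, the SAP's version implies (2 × 10 × 7) + (1 × 10 × 9) = 140 + 90 = 230 scheduled postbaseline HBeAb results, before missed visits. The literal protocol version implies 0.

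**Step 3. How the SAP rules would score HBeAg loss if only reflex testing took place**

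| Situation after HBeAg loss | Baseline HBeAb | Postbaseline HBeAb | Scored as |
|---|---|---|---|
| No confirmed ALT elevation | Missing | Missing | Nonevent, though never tested |
| Reflex test negative | Missing | Negative | Nonevent, on an actual result |
| Reflex test positive | Missing | Positive | Seroconversion, with no evidence of change |

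Seroreversion would need a later negative HBeAb result, so at least two reflex tests in the same participant.

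**Step 4. Who is exposed**

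Phase 1b plans 3 × 10 = 30 participants. Neither document says how many will be HBeAg positive at baseline, and the inclusion criteria set no limit, so the possible range is 0 to about 30. Within that group, the rows that combine HBeAg loss with an HBeAb outcome matter only for those who lose HBeAg. HBeAg loss and confirmed HBeAg loss use HBeAg alone and are unaffected.

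**The case against.** The strongest reply is that HBeAb probably is measured and footnote o is simply incomplete. Several things support this.

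- Table 10 lists HBeAb with no reflex condition, beside the other viral biomarkers. Some tests that 7.7.4 orders only on reflex, such as HAV IgM and HEV IgM, are not in that table.
- The lists are loosely kept in general. Protocol 6.3.5.2 omits the anti-HBsAg antibody that footnote o includes, and SAP Table 3-1 omits the HBV RNA that footnote o includes.
- The SAP says it is based on the eCRF as well as the protocol, and it states outright that HBeAb is collected.
- HBeAb seroconversion is not among the endpoints in SAP 1.1. The analysis is exploratory, and 6.3.3 plans no testing.
- If HBeAb were never run, the baseline HBeAb summary would be empty and the serology listings would show no results, so the gap could be noticed.

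Most of this stands. A reader might infer that the protocol names HBeAb only as a reflex test and that nearly every participant is therefore a nonevent by default. The documents do not support that: Table 10 names the analyte without condition, SAP Table 3-1 says it is collected at every marked visit, and the 6.3.3 table covers only participants HBeAg positive at baseline.

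The reply does not remove the contradiction. Table 10 leaves timing to schedules that give HBeAb none, and a statement in a SAP visit-mapping table does not instruct a site or laboratory to run a test. A reader of the 6.3.3 table alone could not tell untested participants from negative ones.

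**Conclusion.** The documents contradict each other on whether HBeAb is measured at scheduled visits in Cohorts 5-7, and they do not show which version reflects what is run. The size of the disagreement is 0 scheduled postbaseline results per participant on a literal reading of the protocol schedule, against 7 or 9 under SAP Table 3-1.

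The consequence is conditional. If the protocol schedule governs, the HBeAb rows of SAP 6.3.3 count untested participants as nonevents and could count a reflex-only positive as seroconversion. If SAP Table 3-1 governs, the default-nonevent problem does not arise beyond ordinary missed visits or samples, and only the lists are wrong.

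Severity is minor. The rows are exploratory and descriptive, they concern an unstated number of participants (0 to about 30), and no primary or secondary endpoint depends on them.

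**What to change.** Reconcile the lists. Add HBeAb to footnote o of protocol Tables 2 and 3, to the same footnote in SAP Tables 12-2 and 12-3, and to protocol 6.3.5.2, so that it is run on serum already drawn at baseline and at each viral-biomarker visit. Correct the HBV RNA and anti-HBsAg antibody differences between the lists at the same time. The cost is wording plus, if HBeAb is not already being run, one added serology per viral-biomarker visit, a small laboratory expense.

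If HBeAb was not run at scheduled visits and cannot be added, restrict the seroconversion and seroreversion rows of SAP 6.3.3 to participants with a baseline result and at least one scheduled postbaseline HBeAb result, and show that denominator. This costs only SAP wording, though the denominator may be very small or zero.

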7. SAFETY ANALYSES

7.1. Adverse Events and Deaths

Displays for AEs and deaths will be presented separately for each population by treatment group (active group within each cohort and all participants [within population] who received placebo) for the Safety Analysis Set.

7.1.1. Adverse Event Dictionary

Clinical and laboratory adverse events (AEs) will be coded using the current version of Medical Dictionary for Regulatory Activities (MedDRA). System organ class (SOC), high-level group term (HLGT), high-level term (HLT), preferred term (PT), and lower-level term (LLT) will be provided in the AE dataset.

7.1.2. Adverse Event Severity

Adverse events are graded by the investigator as Grade 1, 2, 3, 4, or 5 according to Common Terminology Criteria for Adverse Events (CTCAE), Version 5.0 (November 2017). The severity grade of events for which the investigator did not record severity will be categorized as “missing” for tabular summaries and data listings. The missing category will be listed last in the summary presentation.

7.1.3. Relationship of Adverse Events to Study Drug

Related AEs are those for which the investigator selected “Related” on the AE eCRF to the question of “Related to Study Treatment.” Relatedness will always default to the investigator’s choice, not that of the medical monitor. For this study, relationship is recorded separately for GS-2829/PBO and GS-6779/PBO and for related to any study drug (eg, related to either [or both] of the 2 study drugs). Events for which the investigator did not record relationship to study drug will show the relationship as missing.

7.1.4. Relationship of Adverse Events to Study Procedure

Study procedure related AEs are those for which the investigator selected “Yes” on the AE eCRF to the question of “Related to Study Procedures”. Relatedness will always default to the investigator’s choice, not that of the medical monitor. Events for which the investigator did not record relationships to study procedure will be considered related to study procedure for summary purposes. However, by-participant data listings will show the relationship as missing from that captured on the eCRF.

7.1.5. **Serious Adverse Events**

Serious adverse events (SAEs) will be identified and captured as SAEs if the AEs met the definitions of SAEs that were specified in the study protocol. SAEs captured and stored in the clinical database will be reconciled with the SAE database from the Gilead Patient Safety Department before database finalization.

7.1.6. **Treatment-Emergent Adverse Events**

7.1.6.1. Definition of Treatment-Emergent Adverse Events

Treatment-emergent adverse events (TEAEs) are defined as any AE with a start date on or after the study drug start date; or any AE that led to premature discontinuation of study drug.

7.1.6.2. Incomplete Dates

If the start date of the AE is incomplete and the AE stop date is not prior to the first dosing date of study drug, then the month and year (or year alone if month is not recorded) of start determine whether an AE is treatment emergent. The event is considered treatment emergent if the AE start is the same as or after the month and year (or year) of the first dosing date of study drug.

An AE with completely missing start and stop dates, or with the start date missing and a stop date later than the first dosing date of study drug, will be considered to be treatment emergent. In addition, an AE with the start date missing and incomplete stop date with the same or later month and year (or year alone if month is not recorded) as the first dosing date of study drug will be considered treatment emergent.

7.1.7. **Summaries of Adverse Events and Deaths**

Treatment-emergent AEs will be presented separately for each population and summarized by treatment group (active group within each cohort and all participants [within population] assigned to placebo) for the Safety Analysis Set. For displays of AEs “related to study drug”, events marked as related to either GS-2829/PBO or to GS-6779/PBO in the database will be included. For displays of AEs related to each of the individual study drugs (eg, related to GS-2829 and related to GS-6779), the relatedness for the study drug of interest recorded in the database will be used. For the placebo group, events related to “GS-2829 PBO” or “GS-6779 PBO” will be counted as related to placebo for the viral vector of interest; and only participants taking at least 1 dose of active drug (or placebo for placebo group) for the viral vector of interest will be included in the denominator for the percentage calculations.

7.1.7.1. Summaries of AE Incidence in Combined Severity Grade Subsets

A brief, high-level summary of the number and percentage of participants who experienced at least 1 TEAE in the categories described below will be provided separately for each population by treatment group (active group within each cohort and all participants [within population] assigned to placebo). All deaths observed in the study will also be included in this summary.

- TEAEs
- TEAEs with Grade 3 or Higher
- TEAEs with Grade 2 or Higher
- TEAEs Related to Study Drug
- TEAEs Related to Study Drug with Grade 3 or Higher
- TEAEs Related to Study Drug with Grade 2 or Higher
- TEAEs Related to GS-2829/PBO
- TEAEs Related to GS-2829/PBO with Grade 3 or Higher
- TEAEs Related to GS-2829/PBO with Grade 2 or Higher
- TEAEs Related to GS-6779/PBO
- TEAEs Related to GS-6779/PBO with Grade 3 or Higher
- TEAEs Related to GS-6779/PBO with Grade 2 or Higher
- TE Serious AEs
- TE Serious AEs Related to Study Drug
- TE Serious AEs Related to GS-2829/PBO
- TE Serious AEs Related to GS-6779/PBO
- TEAEs Leading to Premature Discontinuation of Study Drug
- TEAEs Leading to Premature Discontinuation of Study
- Death During the Study

Multiple events will be counted only once per participant in each category.

For the AE categories described below, summaries will be provided separately for each population and will be summarized by treatment group (active group within each cohort and all participants [within population] assigned to placebo), SOC and PT:

- TEAEs by severity
- TEAEs with Grade 3 or Higher, by severity
- TEAEs with Grade 2 or Higher
- TE Treatment-Related AEs, by severity
- TEAEs Related to Each of the Individual Study Drugs
- TE Treatment-Related AEs with Grade 3 or Higher, by severity
- TE Treatment-Related AEs with Grade 2 or Higher
- TE Serious AEs
- TE Treatment-Related Serious AEs
- TEAEs Leading to Interruption of Any Study Drug
- TEAEs Leading to Premature Discontinuation of Any Study Drug

Multiple events will be counted only once per participant in each summary. Adverse events will be summarized first in alphabetic order of SOC, and then by PT in descending order of total frequency for the population within SOC. For summaries by severity grade, the most severe grade will be used for those AEs that occurred more than once in an individual participant during the study.

In addition to the above summary tables, all TEAEs, TE SAEs, and TE treatment-related AEs, will be summarized separately for each population by treatment group (active group within each cohort and all participants [within population] assigned to placebo), and PT only, in descending order of total frequency of PT within population. Preferred terms with the same total population frequency will additionally be sorted in alphabetic order.

In addition, data listings will be provided for the following:

- All AEs, indicating whether the event is treatment emergent
- All SAEs
- All Deaths

- All AEs with severity of Grade 3 or higher
- All AEs leading to premature discontinuation of any study drug
- All AEs for COVID-19 and Suspected COVID-19 infection (eg, identified by COVID-19 Standardized MedDRA Query (SMQ) [narrow scope]).

